6.10.4.1. Hypersensitivity Reactions

A listing of potential hypersensitivity reactions will be provided. For the purpose of this listing, any event satisfying any one of the Anaphylaxis reaction SMQ, Hypersensitivity SMQ, or Angioedema SMQ will be included. Summary tables will be presented only if the number or nature of the events warrants such a comparison.

6.10.4.2. Injection Site Reactions

Injection site reactions are collected in a questionnaire. The following items or other available categories may be collected and summarized for each injection site reaction:

- pain
- itching
- rash
- reaction timing
- swelling
- redness
- erythema
- bruising
- hematoma.

Injection site reactions which meet SAE criteria will also be collected as AEs. If >3% patients have such event occur, then these injection site reactions may be summarized by PT using the version of Medical Dictionary for Regulatory Activities (MedDRA) current at the time of programming.

6.10.4.3. Nausea, Vomiting, and Diarrhea

Nausea, vomiting, and diarrhea event information will be collected on a designated separate eCRF page.

The incidence of nausea, vomiting, and diarrhea will be summarized by the treatment and the time interval of interest. The duration of each event will also be computed in days as event stop date minus event start date. For computation purposes, the end date for ongoing events is the date of last study contact.

The maximum severity and duration from baseline to Week 26 of nausea, vomiting, and diarrhea will be summarized by treatments.

Plot with the % number of subjects with the events vs initiation time course by day and week will also be generated. The y-axis is the % subjects with the specified AE and the x-axis is the time in day or week since the first dose.

A listing with GI TEAEs of interest will be provided.

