9.8.1. Samples for Immunogenicity Research

Samples from patients in each treatment arm will be tested for the development of treatment-emergent LY3298176 antidrug antibodies (ADA), defined as 4-fold increase in titer from baseline. A blood sample will be collected at specific study visits according to the Schedule of Activities (Section 2).

Treatment-emergent positive LY3298176 ADA samples will be evaluated for their ability to neutralize the activity of assigned treatment (LY3298176-neutralizing antibodies). Positive

LY3298176 ADA samples may also be tested for cross-reactivity with native GLP-1 and GIP, and if positive, then for neutralizing antibodies against native GLP-1 and GIP.

All patients will have an ADA sample measured at the follow-up visit (Visit 801) approximately 1 month after the last dose of LY3298176. A risk-based approach will be used to monitor patients who develop treatment-emergent antidrug antibodies (TE-ADA) (defined as >4-fold titer increase over baseline) after treatment with LY3298176. Clinically significant TE-ADA will be defined as any TE-ADA at the follow-up visit (Visit 801) with:

- A high (≥ 1280) or increasing titer
- An association of TE-ADA with a moderate to severe injection site reaction or infusion-related reaction
- Cross-reactive and neutralizing binding of an ADA with endogenous GLP-1 or GIP.

Patients who have clinically significant TE-ADA will be followed with ADA testing every 3 months for approximately 1 year or until the ADA titers have returned to baseline ADA titer (defined as ADA titer within 2-fold of baseline).

Patients followed for at least 1 year since last dose who have not returned to baseline, as defined above, will be assessed for safety concerns and, if no clinical sequelae is recognized by the clinical team, no further follow-up will be required.

Patients who have clinical sequelae that are considered potentially related to the presence of TE-ADA may also be asked to return for additional follow-up testing.

Samples will be retained for a maximum of 15 years after the last patient visit for the study, or for a shorter period if regulations and ERBs impose shorter time limits, at a facility selected by Lilly. The duration allows the sponsor to respond to future regulatory requests related to LY3298176.

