5.1. Study Design and Treatment

Study I8F-MC-GPGB (GPGB) is a randomized, double-blind, parallel, placebo- and active comparator-controlled, Phase 2 multicenter, multi-country study designed to examine the efficacy and safety of once-weekly LY3298176 compared to dulaglutide and placebo in patients with T2DM.

The design for Study GPGB is illustrated in Figure 5.1.

Abbreviations: LY = study drug LY3298176; PK = pharmacokinetics.

Figure 5.1. Study design for I8F-MC-GPGB.

Study procedures and timing for the lead-in, blinded treatment, and follow-up phases are outlined in the schedule of events (appendix 1). Eligibility for this study will be determined at a screening visit (Visit 1). Screening procedures will be performed on approximately Day –21 according to the Schedule of Activities. Patients will receive training on the routine BG monitoring and paper diary completion required during the study. Patients should follow the investigator's instructions related to frequency of SMBG but should test their glucose a

minimum of 3 times per week and as specified for determination of 7-point glucose profiles. Eligible patients will return to the site for some baseline procedures during the lead-in phase and again for randomization to treatment and to receive their first dose of study drug at Visit 3.

After randomization and the first dose (Visit 3), patients will return to the site for PK collection just prior to the second dose (Visit 4). Patients will also have a predose PK collection prior to Week 8 (Visit 10), Week 12 dose (Visit 11), and Week 26 (Visit 16) dose. There will be postdose PK collections after the second dose (PK-specific Visit 5), third dose (PK-specific Visit 7), fifth dose (PK-specific Visit 9, and 12-week dose (PK-specific Visit 12). A safety follow-up visit will occur approximately 4 weeks following the last dose of the study drug. Patients randomized to LY3298176 who develop treatment-emergent anti-LY3298176 antibodies will be monitored after the last visit.

Throughout the study, patients treated with metformin will remain on the same dose they were receiving at Visit 1 unless changes need to be made for safety reasons. All patients will be encouraged to maintain their prestudy diet and exercise levels through the course of the study.

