6.10.4. Adverse Events of Special Interest

Adverse events of special interest to be identified and described during this study are injection site reactions, hypersensitivity reactions, hypoglycemia, acute pancreatitis, major adverse CV events, and selected GI events (nausea, vomiting, and diarrhea).

Descriptive statistics for AESIs will be presented by treatment group and visit. Continuous responses will be summarized using sample size, mean, SD, median, minimum and maximum, while categorical responses will be summarized using sample size, frequency and percentage.

If data warrant, continuous elements of AESIs (such as the duration of hypoglycemaic events) will be analyzed using an MMRM-based model described in Section 6.1.1.

In addition, for AESIs with information collected on the AE eCRF page (that is, hypersensitivity reactions, acute pancreatitis, and major adverse CV events) summary tables will be presented only if >3% of patients has the AESI. The incidence of patients with at least 1 AESI and the patient incidence of AESIs will be summarized, showing frequency and percentage of patients, by SOC (if applicable), PT, and treatment group. The total number of AESIs and the number of AESIs for each SOC (if applicable) and PT will also be reported for each treatment group.

Listings by patient will be provided for AESIs. Listings will also present adjudication information by patient for adjudicated events.

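### Unresolved nausea, vomiting and diarrhea events are closed at last study contact and summarised as complete, so leaving the study while symptomatic shortens the recorded duration

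*SAP*

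**What the plan says.** SAP 6.10.4.3 defines duration event by event: "The duration of each event will also be computed in days as event stop date minus event start date". For events with no stop date it adds: "For computation purposes, the end date for ongoing events is the date of last study contact". It does not define last study contact. The summary is described as follows: "The maximum severity and duration from baseline to Week 26 of nausea, vomiting, and diarrhea will be summarized by treatments".

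SAP 6.10.4 sets the statistics for all adverse events of special interest: "Continuous responses will be summarized using sample size, mean, SD, median, minimum and maximum". If data warrant, continuous elements such as event duration "will be analyzed using an MMRM-based model described in Section 6.1.1". Neither section specifies censoring, a time-to-event method or a count of events still open.

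On follow-up, SAP 5.1 states: "A safety follow-up visit will occur approximately 4 weeks following the last dose of the study drug". In the Schedule of Activities this is Visit 801, Week 30. Protocol 8.2 gives patients who leave early the end-of-study procedures. Protocol 8.1.1 asks patients who permanently stop study drug to remain in the study if possible.

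**The concern.** For an unresolved event, the interval from onset to last contact is only a lower bound on its length. The plan enters it in the mean and median as a finished duration. How far it falls short depends on how long the patient was followed, so the summary mixes symptom duration with length of follow-up. If symptoms drive patients out of the study, the error runs in an unhelpful direction: the arm whose symptomatic patients leave fastest shows the shortest recorded durations.

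The window adds a second problem. The summary is labelled as running to Week 26, but the end-date rule is not tied to Week 26. The SAP does not say whether the label cuts durations at that visit or only selects which events are counted.

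Gastrointestinal tolerability is a named secondary objective (SAP 4.2). Protocol 9.2.1.2 uses these events to judge tolerability across the dose range, and the trial supports Phase 3 dose selection (Protocol 3.1 and 5.4). A duration comparison that favours an arm because its symptomatic patients left would be a poor input to that judgement.

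**Working it through.** **The plan's own figure.** The only related numbers are 10% dropout, 45 completers per arm and 300 randomized (SAP 5.3). 45 / 0.90 = 50 per arm, and 50 x 6 = 300, which reproduces. It allows 50 - 45 = 5 dropouts per arm for all causes. The documents give no figure for event duration, for the share unresolved, or for the rate of leaving while symptomatic.

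**Day arithmetic.** Take an event that starts on Day 42, the first 15-mg dose in Protocol Table GPGB.3, and never receives a stop date.

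- Patient leaves the study at the Week 8 visit (Day 56): 56 - 42 = 14 days.
- Duration cut at Week 26 (Day 182): 182 - 42 = 140 days.
- Last contact at Visit 801 (Week 30, about Day 210): 210 - 42 = 168 days.

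The same unresolved event is thus recorded as 14 days or as 140 to 168, according to follow-up alone. The last two differ by 28 days according to which reading of the section governs.

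**Simulation of early exit.** All inputs here are assumptions: 400,000 events, log-normal durations, onset uniform over Days 0 to 60, and a constant daily probability of leaving the study while symptomatic. Recorded duration is the smaller of the true duration and the time to exit or Visit 801. The true value is the mean duration truncated at Week 26. Shortfall = 1 - recorded / true.

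| Median, log-SD | True mean (days) | 0.2% per day | 1% per day | 2% per day |
|---|---|---|---|---|
| 5, 1.2 | 10.1 | 9.8 (3%) | 8.7 (14%) | 7.7 (24%) |
| 5, 1.5 | 13.7 | 13.1 (4%) | 10.8 (21%) | 9.1 (34%) |
| 10, 1.2 | 19.4 | 18.6 (4%) | 15.4 (21%) | 12.9 (34%) |

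Repeat runs vary slightly, and 3-5% is a fair statement of the low-exit range. At 1-2% per day, 9-26% of events are unresolved. The last row shows the effect between arms: with identical true durations, an arm at 0.2% would show 18.6 days and an arm at 2% would show 12.9.

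The planned median falls less than the mean, but it does fall: by 1-3% at 0.2% per day, 7-13% at 1% and 13-23% at 2%. With unresolved events treated as censored, the Kaplan-Meier restricted mean to Week 26 was 10.1-10.2, 13.9-14.0 and 19.7 days in the three rows, within about 3% of the true value.

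**A second set of assumptions.** Durations are exponential, onset falls in Days 0 to 56, and 5% to 20% of patients with events leave 14 days after onset if still symptomatic. A true mean of 14 days is recorded as 13.7 to 12.9 (2-8% short), 28 days as 27.1 to 24.6 (3-12%), and 60 days as 54.8 to 48.1 (9-20%). In the last case the Visit 801 cut-off alone brings 60 down to 57.0. The direction is the same, and the effect is small for short events.

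**Plausibility of the upper range.** Suppose 25 of the 50 patients in an arm have one event each. Then 9-26% unresolved means 0.09 x 25 = 2.3 to 0.26 x 25 = 6.5 patients leaving with open symptoms. The dropout allowance is 5 per arm for all causes, so the top of the range would exceed it.

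**The case against.** The case against giving this much weight is fair in several respects.

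- **Stopping drug is not leaving the study.** Patients who stop drug are asked to stay, so their events can still receive true stop dates. This stands, and the point is limited to study exit while symptomatic.
- **Follow-up to resolution.** Protocol 9.2 requires follow-up of adverse events that caused drug discontinuation until they resolve, stabilise or are explained. That would soften the problem if it applied. However, Protocol 9.2.1.2.4 keeps non-serious nausea, vomiting and diarrhea off the adverse event form, and Protocol 9.2.1 removes the duty to seek events actively after a patient leaves. Whether the safeguard covers these events is unclear.
- **The median is already planned.** It is less affected than the mean, but not immune.
- **Little rests on duration.** Incidence, maximum severity and the onset plot do not use the imputed end date, and no decision rule is attached to duration. This stands and sets the weight of the point.

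A reader might also infer that antibody monitoring inflates durations in the LY3298176 arms alone. SAP 5.1 says: "Patients randomized to LY3298176 who develop treatment-emergent anti-LY3298176 antibodies will be monitored after the last visit". Protocol 9.8.1 adds: "Patients who have clinically significant TE-ADA will be followed with ADA testing every 3 months for approximately 1 year". The documents do not support that inference. Nothing says that an antibody visit counts as study contact for this purpose. The Schedule of Activities, on which the end-of-trial definition in Protocol 5.3 rests, stops at Visit 801. The duration summary is itself labelled as ending at Week 26, and SAP 7.5 allows immunogenicity data to arrive after the final lock in a separate transfer. The inference also needs one patient with both clinically significant antibodies and an event still open. Even then, later contact with a truly ongoing event reduces the shortfall. Overstatement would need an event that had resolved but was left open on the form.

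**Conclusion.** The concern holds for patients who leave the study while symptomatic, and for the unstated choice between Week 26 and Visit 801. Followed exactly, the rule makes recorded duration depend on how long symptomatic patients in each arm are followed, and it biases duration downward where they leave early.

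The size is not fixed by the documents. Under the log-normal assumptions, the mean is about 3-5% too short at 0.2% exit per symptomatic day and 14-34% too short at 1-2%. The lower part of that span fits the 10% dropout assumption more easily than the top. The window ambiguity is worth 28 days for each event that is still open at Visit 801.

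The consequence is confined to a descriptive tolerability summary; the primary analysis is untouched. This is an inexpensive improvement, not a threat to the trial's conclusions. A differential lengthening through antibody follow-up is not established and forms no part of this conclusion.

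**What to change.** In SAP 6.10.4.3, replace the end-date rule with three statements that apply to all arms:

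1. Every event is truncated at the Week 26 visit or the date of last contact, whichever is earlier.
2. Events unresolved at that date are treated as censored.
3. For each arm, the number of unresolved events is reported together with the Kaplan-Meier median or restricted mean duration to Week 26, in place of the mean of imputed durations.

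Truncation at Week 26 also settles whether post-study antibody visits count as study contact, because they could no longer affect the result.

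The cost is SAP wording and a standard survival summary on data already collected; no clinical procedure changes. There are two small downsides. Restricted means or medians replace simple means. Kaplan-Meier also assumes that patients who leave would have had durations like those who stay, so exit related to how severe or prolonged the event is can still bias the estimate. The count of unresolved events by arm lets the reader judge how much that matters.

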6.10.4.4. Hypoglycemic Episodes and Total Hypoglycemia

Hypoglycemic episodes will be defined as follows: documented symptomatic hypoglycemia, asymptomatic hypoglycemia, probable symptomatic hypoglycemia, nocturnal hypoglycemia, and severe hypoglycemia. Total or overall hypoglycemia is defined as any event meeting the criteria for documented symptomatic hypoglycemia, asymptomatic hypoglycemia, or probable symptomatic hypoglycemia:

- **Documented Symptomatic Hypoglycemia:** Any time a patient feels that he/she is experiencing symptoms and/or signs associated with hypoglycemia and has a plasma glucose level of \leq 3.9 mmol/L (\leq 70 mg/dL).
- **Asymptomatic Hypoglycemia:** An event not accompanied by typical symptoms of hypoglycemia, but with ≤3.9 mmol/L (≤70 mg/dL) plasma glucose.
- Severe Hypoglycemia: An episode requiring the assistance of another person to actively administer carbohydrate, glucagon, or other resuscitative actions. These episodes may be associated with sufficient neuroglycopenia to induce seizure or coma. Plasma glucose measurements may not be available during such an event, but neurological recovery attributable to the restoration of plasma glucose to normal is considered sufficient evidence that the event was induced by a low plasma glucose concentration.
- **Nocturnal Hypoglycemia:** Any hypoglycemic event that occurs between bedtime and waking.
- **Probable Symptomatic Hypoglycemia:** An event during which symptoms of hypoglycemia are not accompanied by a plasma glucose determination (but that was presumably caused by a plasma glucose concentration ≤3.9 mmol/L [≤70 mg/dL]).

• **Total or Overall Hypoglycemia:** Any event meeting the criteria for documented symptomatic hypoglycemia, asymptomatic hypoglycemia, or probable symptomatic hypoglycemia.

Information will be collected on the eCRFs to allow for classification of hypoglycemic episodes into these categories. Note that there is possible overlap among the categories meaning that it is possible for a single event to have >1 classification.

A monthly rate of episodes per patient will be computed by visit, with 1 month defined as a 30-day period. At each applicable visit, the total number of episodes since the previous visit and the number of days since the previous visit will be determined. The monthly rate of episodes will be calculated as the total number of episodes divided by the number of days since the previous visit and multiplied by 30 days. An overall monthly rate will be determined as the total number of episodes over all visits divided by the total number of days between all visits and multiplied by 30 days.

The monthly rate of episodes per patient by visit and overall will be computed for episodes of total hypoglycemia and episodes of nocturnal hypoglycemia. These rates will be summarized by treatment for each visit and overall.

The incidence of hypoglycemic episodes during a time period is defined as the number of patients experiencing at least 1 hypoglycemic episode within that time period. The incidences of total hypoglycemic, nocturnal hypoglycemic episodes and severe hypoglycemic episodes will be determined at each visit (that is, for the time period since the previous visit), and overall (that is, for the time period from first dose of study treatment to last study visit while on study treatment). The incidences for total and nocturnal hypoglycemic episodes will be summarized by treatment for each visit and overall using descriptive statistics (that is, sample size, frequency, and percentage); if a sufficient number of severe hypoglycemic episodes are reported, then incidence of these episodes will also be summarized.

In addition, statistical analyses will be performed for the overall total hypoglycemia (occurred versus did not occur) using a logistic regression analysis with treatment, metformin use (yes, no), and HbA1c strata (<8.5%, $\ge8.5\%$) as fixed effects.

Listings of hypoglycemic episodes of all types will be presented by visit for each patient.

Hypoglycemic episodes occurring after a patient discontinues treatment will be counted in the determinations of rate or incidence of episodes.

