10.3.4.8. Hypoglycemic Episodes

Hypoglycemic episodes will be defined as follows: documented symptomatic hypoglycemia, asymptomatic hypoglycemia, probable symptomatic hypoglycemia, relative hypoglycemia, nocturnal hypoglycemia, and severe hypoglycemia. Total or overall hypoglycemia is defined as any event meeting the criteria for documented symptomatic hypoglycemia, asymptomatic hypoglycemia, or probable symptomatic hypoglycemia.

The total hypoglycemia monthly rate per patient will be summarized where 1 month is defined as a 30-day period. This will be calculated by dividing the total number of hypoglycemic events by the total number of days between visits and multiplying by 30 days. This rate will also be calculated per patient for nocturnal hypoglycemia episodes, and summarized by treatment.

The incidence and rate of total hypoglycemic episodes and nocturnal hypoglycemic episodes will be presented for each visit (incidence between visits) and overall. Nocturnal hypoglycemia episodes are episodes that occur between bedtime and waking. The incidence of hypoglycemic episodes during a time period on treatment is defined as patients with at least 1 hypoglycemic episode occurring within that period of time. Statistical analyses will be performed for overall total hypoglycemia using a logistic regression analysis with fixed effects of treatment, metformin use, and HbA1c strata.

Listings of hypoglycemic episodes and severe hypoglycemic episodes will be presented by visit for each patient. If a sufficient number of severe hypoglycemic episodes are reported, then incidence summaries similar to incidence of hypoglycemic episodes will be included.

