5.3. Determination of Sample Size

Approximately 300 patients will be randomized to placebo, dulaglutide, or 1 of the 4 LY3298176 treatment arms assuming a 10% dropout rate resulting in approximately 45 completers per arm.

The Bayesian approach using a dose-response model with respect to an HbA1c change from baseline to 26 weeks will provide approximately 98% probability to show with 90% confidence that at least 1 LY3298176 dose has superior glycemic control over placebo with a superiority bound of -0.8%. The sample size also provides >95% probability to show with 80% confidence that at least 1 LY3298176 dose has non-inferior glycemic control compared with dulaglutide from baseline to 26 weeks with a 0.3% non-inferiority bound. This assumes a profile for the change in HbA1c from baseline to 26 weeks shown in Table 5.1, and a standard deviation (SD) of 1.0%.

In addition, this sample size also provides approximately 89% probability to show with 60% confidence that at least 1 LY3298176 dose has superior weight loss compared with dulaglutide from baseline to 26 weeks with a superiority bound of -2 kg. This assumes a profile for the change in body weight from baseline to 26 weeks shown in Table 5.1, and an SD of 6 kg.

Table 5.1. Dose-Response Assumption Used in Sample Size Determination

	Placebo	LY 1	LY 5	LY 10	LY 15	Dulaglutide
CFBL HbA1c (%)	0%	-0.74%	-1.17%	-1.29%	-1.44%	-1.28%
CFBL Body Weight (kg)	0	-2.0	-3.0	-5.0	-6.0	-2.5

Abbreviations: CFBL = change from baseline; HbA1c = hemoglobin A1c; LY = study drug LY3298176.

6. A Priori Statistical Methods

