6.10. Safety Analyses

Safety analyses will be performed on the safety population and classified by the actual treatment group unless specified. Safety descriptive statistic summaries may also include all LY3298176 doses combined if appropriate. Unless specified otherwise, safety listings will display values/events during all study periods; key adverse events (AEs) summaries will be presented separately for the treatment period and for the treatment period and follow-up period combined if applicable. Any events/values reported after start of rescue therapy but before the start of the follow-up period will be included in safety analyses for the treatment period.

Safety measures will include extent of exposure, vital signs, physical characteristics, treatment-emergent adverse events (TEAEs; including serious adverse events [SAEs]), adverse events of special interest (AESIs; that is, injection site reactions, hypersensitivity reactions, hypoglycemia episodes, GI events - nausea, vomiting, and diarrhea-, acute pancreatitis, and major adverse cardiovascular [CV] events), laboratory measures (including hematology, chemistry, urinalysis, and samples collected for testing for anti-LY3298176 and antibodies), and electrocardiograms (ECGs). In addition, the change from baseline to 26 weeks in HDL-C, total cholesterol, triglycerides, and LDL-C will be analyzed on the mITT population.

The summary statistics for continuous variables will be sample size, mean, SD, median, minimum, and maximum. If applicable (for example, in the case of MMRM analyses) these descriptive statistics may also include LS means, LS means standard error (SE), and 95% CI for each treatment group as well as for LY3298176 difference from placebo.

The summary statistics for categorical variables will be sample size, frequency, and percentage.

Additional analyses, such as concentration-safety lab plots, may be performed if warranted upon review of the data.

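### The overall hypoglycemia rate by arm carries no exposure weighting and has no planned between-arm model; total episodes over total patient-time should be reported

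*SAP*

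**What the plan says.** The rate is built at patient level. SAP 6.10.4.4 begins: "A monthly rate of episodes per patient will be computed by visit, with 1 month defined as a 30-day period". It defines the overall figure as the "total number of episodes over all visits divided by the total number of days between all visits and multiplied by 30 days". The next paragraph ties both versions to the patient ("The monthly rate of episodes per patient by visit and overall will be computed", for total and for nocturnal episodes), and then comes the arm-level step: "These rates will be summarized by treatment for each visit and overall". Protocol 10.3.4.8 has the same unit: "The total hypoglycemia monthly rate per patient will be summarized where 1 month is defined as a 30-day period".

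Section 6.10.4.4 does not say which statistic summarises the patient rates. The default is in SAP 6.10: "The summary statistics for continuous variables will be sample size, mean, SD, median, minimum, and maximum". Neither document names a weight, a pooled person-time rate or a count model for hypoglycemia.

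The one specified test is of occurrence: "statistical analyses will be performed for the overall total hypoglycemia (occurred versus did not occur) using a logistic regression analysis". Its terms are treatment, metformin use and HbA1c stratum, with no term for length of follow-up. Yet SAP 4.2 lists the rate of hypoglycemia, alongside its incidence, within a secondary objective, and Protocol 10.3.4.1 undertakes to report pairwise comparisons of each LY3298176 dose with placebo and with dulaglutide for the safety analyses.

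**The concern.** A rate from 14 days of observation is a far noisier number than one from 182 days, but an unweighted mean gives them equal say. The median offers little help: if fewer than half of an arm has any episode, it is zero. The test on occurrence uses neither repeat episodes nor time at risk, so no specified analysis puts a properly weighted rate beside a comparison between arms.

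What is at stake is how the arms' hypoglycemia rates are read when doses are chosen for Phase 3. The rate is descriptive and no decision rule depends on it.

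**Working it through.** **Inputs from the documents.** 300 patients, six equal arms, and "assuming a 10% dropout rate resulting in approximately 45 completers per arm" (SAP 5.3): 300/6 = 50 per arm, and 50 × 0.90 = 45 completers, which reproduces the plan's figure. Full treatment follow-up is 26 weeks, or 182 days.

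**Assumptions, because the documents are silent.** Timing of the 5 exits per arm; an episode rate L per 30 days of 0.02, 0.1 or 0.3; a between-patient (gamma) variance parameter k of 0, 1, 3 or 10, where k = 0 is Poisson.

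**Weight of one episode.**
- Patient followed 14 days: 30/14 = 2.14 per 30 days; divided by 50, it adds 0.043 to the arm mean.
- Completer: 30/182 = 0.165; divided by 50, it adds 0.0033, which is 13 times less (182/14).
- Pooled rate with five exits at day 14: total time is 45 × 182 + 5 × 14 = 8,260 days, so any one episode adds 30/8,260 = 0.0036.
- Those five patients hold 10% of the weight in the mean and 70/8,260 = 0.85% of the time.

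**Precision.** With T_i as follow-up in 30-day units:
- mean of patient rates: Var = (1/n²) Σ(L/T_i + kL²)
- pooled rate: Var = Σ T_i²(L/T_i + kL²) / (ΣT_i)²

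For k = 0 the rate cancels. In weeks, with all exits at Week 2: (45/26 + 5/2)/50² = 0.001692 against 1/(45 × 26 + 5 × 2) = 1/1,180 = 0.000847. The SE ratio is √(0.001692/0.000847) = 1.41. The same steps give 1.19 for Week 4 and 1.07 for Week 8.

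SE ratios (mean of patient rates / pooled) at L = 0.1:

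| Five exits per arm | k=0 | k=1 | k=3 | k=10 |
|---|---|---|---|---|
| all at day 14 | 1.41 | 1.26 | 1.14 | 1.03 |
| days 14, 28, 56, 84, 140 | 1.15 | 1.09 | 1.04 | 1.00 |
| all at day 91 | 1.02 | 1.01 | 1.00 | 0.99 |

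The k = 10 column depends on L. At L = 0.02 it reads 1.19, 1.06 and 1.00; at L = 0.3 it is 0.99 throughout.

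**Bias.** With a constant rate and dropout unrelated to it, both estimators have expectation L, so there is none. Suppose instead that the rate is three times higher in the first 4 weeks (later rate set to 1):
- Full 26-week average: (4 × 3 + 22)/26 = 1.308. A patient leaving at Week 2 or 4 averages 3.
- Mean of patient rates: (45 × 1.308 + 5 × 3)/50 = 1.477, or 13% too high.
- Pooled, exits at Week 2: (45 × 34 + 5 × 6)/1,180 = 1.322, or 1.1% too high. Exits at Week 4: (45 × 34 + 5 × 12)/1,190 = 1.336, or 2.2%.
- Exits spread as in the table (at a later rate of 0.1): 0.1398 and 0.1326 against 0.1308, or 7% and 1.4%.

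The sign can reverse. If the early rate is half the later one, the full average is (4 × 0.5 + 22)/26 = 0.923 and the mean of patient rates is (45 × 0.923 + 5 × 0.5)/50 = 0.881, about 5% too low.

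If patients leaving at day 14 have three times the rate of the others, the two summaries give 0.120 and 0.102 per 30 days when completers have 0.1. Here they describe different things: the average patient's rate, and episodes per unit of observed time.

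**The case against.** The strongest reply is that the text is unclear more than it is wrong. Section 6.10.4.4 never says mean. That word comes from the default list, which also gives the median and range, and the sentence defining the overall rate could on its own be read as a ratio of arm totals. This stands as a caution, but the following paragraph makes the rate per patient, and if a pooled rate was intended the SAP needs to say so.

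A reader might infer that the arm rates will be noisy and tilted by early dropouts, most of all at the higher doses. The documents do not support that. They give no timing of dropout, no expected episode rate and no relation of dropout to dose. Protocol 8.1.1 asks that patients who stop study drug remain in the study if possible, so only those who leave the study have short denominators. There is some reason to doubt a constant rate, since the 15-mg arm reaches its target only at dose 7 (day 42, Protocol Table GPGB.3), but that does not settle the direction.

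Other planned output helps. By-visit rates compare patients over similar intervals, so the point concerns the overall rate. Episodes are listed by patient, and SAP 6.6 gives patient-years by arm. Those patient-years run from first dose to 7 days after last dose, however, while 6.10.4.4 counts episodes after treatment discontinuation, so numerator and denominator would not match.

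Finally, SAP 6.10.4 permits an MMRM for continuous elements of events of special interest where the data justify it. Its example is duration; it is optional and does not commit to comparing rates.

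**Conclusion.** The plan summarises per-patient rates by arm without exposure weighting and specifies no model comparing rates, although the rate belongs to a secondary objective. That an unweighted mean will be among the summaries rests on the SAP 6.10 default.

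The size is conditional. At the planned 10% dropout the SE ratio runs from 1.41 (all exits at Week 2, Poisson), through about 1.15 (exits spread, Poisson), to about 1.0 (late exits, or strong between-patient variation unless episodes are rare). Bias is possible only with a rate that changes over time or dropout related to hypoglycemia; the 13% against 1–2% illustrates one assumed case and is not a prediction. The point justifies an inexpensive improvement to the SAP and does not put the trial's main conclusions in doubt.

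**What to change.** In SAP 6.10.4.4:

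- Report each arm's overall rate as total episodes divided by total patient-time at risk, for total and for nocturnal hypoglycemia. Keep the per-patient rates as a listing.
- Define time at risk so that it matches the episodes counted. Days after treatment discontinuation belong in the denominator if episodes then are in the numerator, and the text should say whether the safety follow-up period is included. The overall incidence, now limited to visits on study treatment, needs to be reconciled with the same counting rule.
- Add a negative binomial regression with treatment, metformin use and HbA1c stratum, and log days at risk as offset, giving each dose against placebo and dulaglutide. If episodes are few, fall back to pooled rates with exact intervals.

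The cost is SAP wording and one standard model; episodes and days are already computed per patient. The model may not be estimable with sparse events, and an offset does not remove bias from dropout that depends on hypoglycemia.
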